11.6 Up to 3 Days Prior to the Index Procedure

The following preprocedural data of all subjects shall be collected within up to 3 days prior to the index procedure:

- Current antiplatelet medication
- Current cardiac medications; collection is only required for subjects with any changes of cardiac medications
- 12 lead Electrocardiogram (ECG)
- Collection of the latest PCI procedure information, including treated vessel, location and procedure type
- Laboratory detection
 - Total CK or CK-MB (if the total CK is $>1\times$ ULN, CK-MB or troponin must be run)
 - Troponin (if CK / CK-MB cannot be run)

It is recommended that the same type of cardiac enzyme shall be collected prior to and after the procedure during the hospitalization (i.e., not converting from CK-MB to troponin, or vice versa).

Note: preprocedural cardiac enzymes can be drawn from the sheath at the time of sheath insertion.

11.7 Enrollment and Index Procedure

Use the standard catheter puncture technique to perform the procedure. The time of inserting the first guiding catheter is the start time of the procedure.

During the procedure, the following operation and assessment shall be completed:

- coronary artery angiography: all patients shall receive angiography assessment in the procedure according to standard clinical routine practice. Angiography data and films of enrolled subjects , as well as working records of technical personnel shall be submitted to Angiographic Core Laboratory for qualitative and quantitative analysis, including the confirmation of the guidewire's entry into the vessel subintimal. Angiography data and films of intervention on

non-target vessel in the index procedure do not need to be submitted to Angiographic Core Laboratory.

- Confirm the lesion meets the inclusion criteria of angiography and fails to meet any exclusion criterion of angiography.
-
- When BridgePoint CTO device facilitates a guidewire to cross the target lesion and the guidewire is confirmed to locate in the true vessel lumen or distal collateral branch vessel lumen of target lesion, all subjects shall receive PCI treatment on the target lesion according to local clinical practice, such as using balloon catheters to make pre-dilation, stent implantation, etc., to target lesion.

In this study, before the failure of BridgePoint CTO System device, other devices against CTO (such as Frontrunner, Crosser or SafeCross, etc.) shall not be used, but the intravascular ultrasound-guided true-lumen seeking and tracking (IVUS-TST) is allowed, i.e., the technique in which the guidewire can cross (or re-cross) the true lumen and move forward along the true lumen to the distal vessel under the guidance of IVUS and taking the occluded segment as the target.

11.8 End of Procedure / Prior to Hospital Discharge

The end time of procedure is defined as the time of removing the guiding catheter (after the final angiography). The following steps shall be completed after removing the catheter sheath according to local clinical routine practice:

- Record information of target lesion, guidewire and balloon catheter used, and information of pre-dilation, post-dilation (if applicable) and stent implantation and other information on corresponding eCRFs.
- Record procedure information on corresponding eCRFs, including start and end time of procedure, total fluoroscopy time of X-ray, total contrast dose used in the procedure, etc.
- Collect current cardiac medications: collection is only required for subjects with any changes of cardiac medications.
- Record anticoagulation and antiplatelet medications during the procedure.
- As described in section 24, complete recording and assessment of adverse events in the procedure and and collect source documents.
- 12 lead ECG within 1 day post procedure
- Laboratory detection
 - At least one CK Total or CK-MB draw must be obtained within 1 day after the index procedure. If the CK Total value is abnormal, CK-MB must be run.
 - If CK/CK-MB is not used, the troponin shall be run.

Note: it is recommended that the same type of cardiac enzymes shall be collected prior to and after the procedure during the hospitalization.

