4.3.3.3 Primary Safety Endpoint

It was adjudicated by the Data and Safety Monitoring Committee (DSMC) that eight adverse events occurred on seven subjects met the definition of major adverse cardiac events (MACE), the primary safety endpoint. The incidence of 30-day MACE 4.8%, which is lower than the acceptable rate of 8.5% as described in clinical investigation plan (CIP), so that it can refuse a null hypothesis of 30-day MACE rate of 14% (p value is 0.0003). Therefore, FAST-CTO study met its primary safety endpoint. Table 4-6 summarizes 30-day MACE and components of 30 days MACE.

Table 4-7: 30-Day MACE

Subject Events	Total (n=147)
MACE	4.8% (7/147)
Cardiac death	1.4% (2/147)
Q-wave MI	0.0% (0/147)
Non-Q-wave MI	4.1% (6/147)
Non-Q-wave MI ^a	4.2% (6/143)
Target lesion revascularization	0.0% (0/147)
Emergency CABG	0.0% (0/147)

^a Excluding subjects that had no blood drawing or only one blood drawing in 6-8 hours.

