g: A minimum of 1 CK Total or CK-MB draw must be obtained within 1 day after the index procedure. If CK Total values are abnormal (>1× ULN), CK MB or troponin must be run.

h: If neither CK Total nor CK-MB is drawn, troponin must be drawn.

i: Collection is only required for subjects with any changes of cardiac medications.

j: All AEs will be monitored and reported to BSC from the time of enrollment through the 12-month follow-up for all subjects enrolled

k: ADEs, SAEs, SADEs, UADEs, USADEs, and device deficiencies will be monitored and reported to BSC from the time of enrollment through the 12-month follow-up for all subjects enrolled.

Abbreviations: AE= Adverse event; ADE= Adverse device effect; CBC= Complete blood count; CK= Creatine Kinase; CKMB= Creatine kinase isoenzyme; ECG= Electrocardiogram; PCI= Percutaneous coronary intervention; SADE= Severe adverse device effect; SAE= Severe adverse event; UADE=Unanticipated adverse device effect; USADE= Unanticipated severe adverse device effect

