11.11 Source Documents

Where copies of the original source document as well as printouts of original electronic source documents are retained, it is required that the copies be signed and dated by a member of the investigation center team with a statement that it is a true reproduction of the original source document

12. Statistical Considerations

Study Endpoint

Primary Effectiveness Endpoint

Technical success is defined as the ability of the BridgePoint Medical System to successfully facilitate placement of a guidewire beyond a CTO lesion in the true vessel lumen/within the collaterals

Safety Endpoint

30 days MACE is defined as cardiac death, Q-wave and non-Q-wave myocardial infarction (total CK is two times larger than normal upper limit and MB score is positive) and ischemia driven target lesion revascularization (TLR) .

Additional Study Endpoints

- Procedure success: is a mean lesion diameter stenosis <50% in 2 near-orthogonal projections with TIMI 2-3 flow, as visually assessed by the physician, without the

occurrence of in-hospital Q wave MI, TLR, or cardiac death.

- Total procedure time, and the definition is the time from inserting the first guiding catheter to withdrawing the last guiding catheter minus the procedure time for determining the refractoriness of a lesion.
- Total time (i.e., total time of X-ray measured by site fluoroscopy system minus X-ray time for determining refractoriness of a lesion) and total radiation dose (mSv)
- Total contrast dose
- Rate of MACE at 30 days, 6 months and 12 months
- Rate of stent thrombosis (ST) at 30 days, 6 months and 12 months
- Rate of cardiac tamponade before hospital discharge
- Rate of kidney failure caused by contrast before hospital discharge

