Lesion Location

Lesion location is the location of the lesion according to the specific coronary artery (i.e., left main, LAD, LCX, or RCA) or bypass graft, and is specified as proximal, mid, or distal. A standard map will be provided to be used for location descriptions.

Leukopenia

Leukopenia is a leukocyte count of $<3.0 \times 10^9/\text{liter}$ for more than 3 days.

Malfunction

A malfunction is a failure of the device to meet performance specifications or otherwise perform as intended.

Myocardial Infarction

The definition of myocardial infarction in FAST-CTO China clinical trial:

Spontaneous myocardial infarction²⁵ (> 72 hours post procedure):

Detection of rise and/or fall of cardiac biomarkers (CK-MB or troponin) with at least one value above the 99th percentile of the upper reference limit (URL) together with evidence of myocardial ischemia with at least one of the following:

- Symptoms of ischemia;
- ECG changes indicative of new ischemia (new ST-T changes or new left bundle branch block [LBBB]);
- Development of pathological Q waves in the ECG;
- Imaging evidence of new loss of viable myocardium or new regional wall motion abnormality.

Percutaneous Coronary Intervention (PCI) and Coronary Artery Bypass Graft (CABG) related Myocardial infarction ²⁶ (≤ 72 hours post procedure)

1. CK-MB in patients with normal baseline concentration reaches any of the following criteria:

- An increase in CK-MB peak to $\geq 10X$ URL during the first 48 hours following the procedure
- An increase in CK-MB peak to $\geq 5X$ URL during the first 48 hours following the procedure, plus new pathological Q-wave in at least 2 contiguous leads, or new persistent LBBB

Or meets any of the following criteria if CK-MB levels are unavailable and baseline troponin concentrations are normal:

- An increase of troponin (I or T) to $\geq 70X$ URL during the first 48 hours following PCI
- An increase of troponin (I or T) to $\geq 35X$ URL during the first 48 hours following PCI, and development of new pathological Q-wave in at least 2 contiguous leads or new persistent LBBB

2. In patient with elevated baseline CK-MB (or troponin) in whom the biomarker levels have shown the tendency to be stable or decrease, if the CK-MB (or troponin) rises by an absolute increment equal to those levels recommended above from the most recent pre-procedure level.

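### One enzyme draw within a day meets the protocol minimum, while periprocedural MI is defined on a 48-hour CK-MB peak: 30-day MACE can be under-counted, and the SAP has no analysis that would show it

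*Protocol*

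**What the plan says.** **Sampling.** Protocol 11.8 sets the post-procedure minimum: "At least one CK Total or CK-MB draw must be obtained within 1 day after the index procedure". Footnote g of Table 11.1-1 sets the same minimum. Neither fixes a time within that day, asks for a repeat, or requires anything in hours 24 to 48. Troponin stands in only where neither CK test is used.

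**Follow-on test.** The two places differ. Section 11.8 says "If the CK Total value is abnormal, CK-MB must be run". Footnote g, once total CK exceeds the upper limit of normal, says "CK MB or troponin must be run". Neither asks for a new sample.

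**MI definition.** Protocol 7.1 refers the MI component of MACE to section 31.2. There, with a normal baseline, PCI-related MI is a CK-MB peak of at least 10 times "URL during the first 48 hours following the procedure", or at least 5 times with a new Q wave or persistent LBBB. Troponin (70 or 35 times) applies only when CK-MB is unavailable. Protocol section 12, Safety Endpoint, instead describes the MI component as "total CK is two times larger than normal upper limit and MB score is positive".

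**Analysis.** SAP 3.1 gives 30-day MACE as a count, a percentage and a binomial 95% CI, in ITT and PP. Neither set in SAP 4.1 has a biomarker condition. SAP 7.3 rules out imputation and gives rules only for missing event dates.

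**Precedent.** The FAST-CTO 30-day MACE table in Protocol 4.3.3.3 reports non-Q-wave MI a second time, with the note "Excluding subjects that had no blood drawing or only one blood drawing in 6-8 hours".

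**The concern.** A single value taken at an unspecified time need not be the peak. If it falls before or after the peak, a subject whose CK-MB did cross the threshold can show a value below it. The 10-times criterion needs no symptom or ECG change, so such an MI can be silent. Two safeguards might be expected to catch it. The CEC (Protocol 27.3 and 31.2) works on reported cases and cannot adjudicate a rise that nobody measured. Later contacts (Protocol 11.9) may be by telephone and collect no enzymes.

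What is at stake is the primary safety estimate. The study tests no hypothesis (SAP 3.1.1), so the MACE rate and its CI are the safety result. If sites differ in when and how often they draw blood, ascertainment differs with them. FAST-CTO also showed its MI rate without thinly sampled subjects; here a subject with one draw is fully compliant and the SAP has no matching analysis.

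**Working it through.** **1. Reproduce the documents' figures (Protocol 4.3.3.3).** MACE 7/147 = 4.76%. Non-Q-wave MI 6/147 = 4.08%, and 6/143 = 4.20% after the exclusion. Exact binomial P(X ≤ 7 | n = 147, p = 0.14) = 0.00025, which agrees with the stated 0.0003.

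**2. Separate the MACE subjects.** The table gives 6 subjects with non-Q-wave MI, 2 with cardiac death, and none with Q-wave MI or TLR: 6 + 2 = 8 events in 7 subjects. So 8 − 7 = 1 subject had both. MI was present in 6/7 (86%) and was the only component in 5/7 (71%). In the EU trial (Protocol 4.2.5.3) both MACE events (2/42) were non-Q-wave MI.

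**3. Direction.** The largest of the values measured cannot exceed the true 48-hour peak. Against a fixed threshold on that peak, too few draws can turn an MI into a non-MI but not the reverse. This covers the timing and number of draws. The choice between CK-MB and troponin is a separate question, and the documents do not settle its direction.

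**4. Size.** Let s be the share of qualifying MIs detected. The documents give no value, so s = 0.5 to 0.9 is an assumption. The two subjects who died remain MACE cases whatever s is.

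- Observed MI = s × 6/147
- Observed MACE = (2 + 5s)/147
- Relative change in MACE = (2 + 5s)/7 − 1

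| s | Observed MI | Observed MACE | Relative change |
|---|---|---|---|
| 1.0 | 4.08% | 4.76% | 0 |
| 0.9 | 3.67% | 4.42% | −7% |
| 0.7 | 2.86% | 3.74% | −21% |
| 0.5 | 2.04% | 3.06% | −36% |

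With 100 subjects, the chance of seeing no MI at all is (1 − 0.0408s)^100: 1.5% at s = 1.0, 3.6% at s = 0.8 and 12.7% at s = 0.5.

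**5. What an evaluable-sample row would show.** Suppose 4 MIs are seen among 100 subjects, all in evaluable subjects (Clopper-Pearson 95% CI):

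- none non-evaluable: 4/100 = 4.0% (1.1–9.9)
- 10 non-evaluable: 4/90 = 4.4% (1.2–11.0)
- 20 non-evaluable: 4/80 = 5.0% (1.4–12.3)
- 50 non-evaluable: 4/50 = 8.0% (2.2–19.2)

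**The case against.** The case on the other side has several parts.

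- **It is only a minimum.** Sites may draw more often, an ECG within a day is mandatory, all adverse events are collected, and a CEC adjudicates. This stands. A reader might infer that MIs will in fact be missed; the documents show only that they can be.
- **Total CK is not enough by itself.** A reader might infer that a total CK result alone always suffices. It does so only when normal. The gap lies in timing and the lack of a repeat more than in the choice of marker.
- **Nothing says such subjects are recorded as MI-free.** Correct. That they would count as event-free is an inference from a plain count with no rule for inadequate sampling. The CEC charter and the eCRF are not among the documents.
- **Under section 12, total CK followed by CK-MB is a coherent test.** Also fair: how adequate the sampling is depends on which definition governs. But Protocol 7.1 points to 31.2, and the two must be reconciled in any case.
- **Separate troponin thresholds are deliberate.** Agreed; 10 times against 70 times is not itself a contradiction. What remains is that 11.8 and footnote g allow different markers after an abnormal CK.
- **FAST-CTO's restricted analysis barely moved the rate**, from 4.1% to 4.2%. True, but it removed only 147 − 143 = 4 subjects. Here, subjects sampled at the minimum could fall into that excluded category, so the share affected could be much larger.
- **No test or success criterion changes.** True. The effect is on the estimate and its interval.

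**Conclusion.** The concern holds in this form: under the section 31.2 definition, the minimum sampling allows periprocedural MI to be under-ascertained, with bias only downward, and no planned analysis would reveal it. With FAST-CTO's rates and an assumed detection of 50–90%, MI of 4.1% would be seen as 2.0–3.7%, and MACE of 4.8% as 3.1–4.4%.

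Three limits apply. The detection range is an assumption. FAST-CTO's MI definition is not given, so neither its rates nor MI's share of MACE need carry over to the 31.2 thresholds. And a reader might subtract every missed MI from MACE and reach 4.76 − 4.08 + 2.04 = 2.7% at 50% detection; that wrongly drops the subject who also died, and 3.1% is the figure the documents support.

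This should be corrected. The conflict between section 12 and section 31.2, and that between 11.8 and footnote g, need reconciling whatever view is taken of the size.

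**What to change.** 1. **One MI definition.** Reconcile Protocol section 12 with section 31.2 so that a single definition governs the primary safety endpoint.
2. **One sampling rule.** Make 11.8 and footnote g agree. Set a common post-procedure window for the draw already required, run CK-MB on it (troponin only where CK-MB is unavailable, as 31.2 provides), and record the sample time. State that one timed draw standardises ascertainment but does not establish the 48-hour peak.
3. **One SAP table (section 3.1).** Report 30-day MACE and non-Q-wave MI for all subjects and again for biomarker-evaluable subjects, with evaluability defined before analysis by marker, window and number of draws. Tabulate subjects with no draw, one draw and more than one. Do not describe inadequately sampled subjects as confirmed MI-free. Show the two rates side by side: if extra draws follow symptoms, the evaluable rate may run high.

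**Cost.** Parts 1 and 2 need a protocol amendment with IRB/EC approval (Protocol section 13), minor site scheduling and a CK-MB assay on an existing sample, but no extra draw. Part 3 is one table and can be added under SAP 5.12 before analysis, even if enrolment is complete. The reported MACE rate may be higher as a result.

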11.9 Follow-up

All subjects will receive assessments at the following points;

- 30-day follow-up (30 ± 7 days)
- 6-month follow-up (180 ± 30 days)

- 1-year follow-up (365 ± 30 days)

Follow-up may be performed via telephone interview or clinical visit. The following data will be collected at each follow-up visit:

- Collection and assessment of adverse events during the follow-ups, as well as collection of the source documents, as described in section 24
- Current angina condition assessment
- Current antiplatelet medications (aspirin and thiophene pyridines). Information on dose change, medication interruption and discontinuation must be recorded.
- Current cardiac medications: collection is only required for subjects with any changes of cardiac medications.

11.9.1 Loss to Follow-up

If a subject cannot return for follow up or cannot be contacted through telephone, at least 3 telephone contacts shall be made to obtain necessary information of the subject. All attempts shall be recorded in source documents. If a subject does not respond to 3 telephone follow-ups, a letter must be sent to the subject in registered post subsequently. If a subject does not respond to the letter, this subject shall be considered as a “loss to follow-up” of current study treatment or telephone contact. Investigators must attempt to contact the subject at each follow-up point and a registered mail shall be sent again if the subject cannot be contacted after 3 telephone contacts. Only after the subject cannot be contacted at the last follow-up, the subject shall be considered as a loss to follow-up and a study end form shall be filled.

11.10 Study End

A 12 months follow-up will be conducted to all subjects after the procedure. In order to assess the study endpoint, 12 months follow-up data of each subject must be collected.

11.11 Source Documents

Where copies of the original source document as well as printouts of original electronic source documents are retained, it is required that the copies be signed and dated by a member of the investigation center team with a statement that it is a true reproduction of the original source document

12. Statistical Considerations

Study Endpoint

Primary Effectiveness Endpoint

Technical success is defined as the ability of the BridgePoint Medical System to successfully facilitate placement of a guidewire beyond a CTO lesion in the true vessel lumen/within the collaterals

Safety Endpoint

30 days MACE is defined as cardiac death, Q-wave and non-Q-wave myocardial infarction (total CK is two times larger than normal upper limit and MB score is positive) and ischemia driven target lesion revascularization (TLR) .

Additional Study Endpoints

- Procedure success: is a mean lesion diameter stenosis <50% in 2 near-orthogonal projections with TIMI 2-3 flow, as visually assessed by the physician, without the

occurrence of in-hospital Q wave MI, TLR, or cardiac death.

- Total procedure time, and the definition is the time from inserting the first guiding catheter to withdrawing the last guiding catheter minus the procedure time for determining the refractoriness of a lesion.
- Total time (i.e., total time of X-ray measured by site fluoroscopy system minus X-ray time for determining refractoriness of a lesion) and total radiation dose (mSv)
- Total contrast dose
- Rate of MACE at 30 days, 6 months and 12 months
- Rate of stent thrombosis (ST) at 30 days, 6 months and 12 months
- Rate of cardiac tamponade before hospital discharge
- Rate of kidney failure caused by contrast before hospital discharge

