7.1 Primary Study Endpoint

- Technical Success: the ability of the BridgePoint Medical System to successfully facilitate placement of a guidewire beyond a CTO lesion in the true vessel lumen/within the collaterals
- 30-day MACE rate for CTO cases in which the BridgePoint Medical System was used

MACE is defined as the composite of cardiac death, Q-wave and non-Q-wave myocardial infarction, and any ischemia-driven target lesion revascularization. (for MI definition please refer to section 31.2)

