3. In patient with elevated baseline CK-MB (or troponin) in whom the biomarker levels have not shown to be stable or decrease, if the CK-MB (or troponin) rises by an absolute increment equal to those levels recommended above from the most recent pre-procedure level, plus new ST-segment elevation or depression and clinical symptoms related to myocardial infarction, such as new or aggravated heart failure or persistent hypotension.

New York Heart Association classification

- Class I: Patients with no limitation of activities; they suffer no symptoms from ordinary activities
- Class II: Patients with slight, mild limitation of activity; they are comfortable with rest or with mild exertion
- Class III: Patients with marked limitation of activity; they are comfortable at rest
- Class IV: Patients who should be at complete rest, confined to bed or chair; any physical activity brings on discomfort and symptoms occur at rest

Perforation

Perforations are classified as follows:

- Angiographic perforation: Perforation detected by clinical site or Angiographic Core Laboratory at any point during the procedure.

- Clinical perforation: Perforation requiring additional treatment, including efforts to seal the perforation or pericardial drainage, or resulting in significant pericardial effusion, abrupt closure, MI, or death.
- Pericardial hemorrhage/tamponade: Perforation causing tamponade.

Prolonged Angina Pectoris

Prolonged angina pectoris is angina lasting longer than 1 hour.

Pseudoaneurysm

A pseudoaneurysm is an encapsulated hematoma in communication with an artery. It is often difficult to distinguish from an expanding hematoma at the site of arterial puncture. It usually requires surgical repair.

Randomization

Randomization is the procedure by which subjects are assigned to a treatment group based on appropriate theories of probability including those involving random chance and conditional assignments.

Reference Diameter of Normal Arterial Segment

Reference diameter of the normal artery segment is an angiographic measurement of the artery proximal and/or distal to the lesion intended for angioplasty. This is also referred to as “reference vessel diameter” (RVD).

Repeated Intervention

Repeat intervention is a PCI or CABG performed after the end of the index procedure. The repeat intervention should be performed to improve blood flow.

Restenosis Lesion

A restenosed lesion is a previously treated lesion that again has a stenosis.

Restenosis

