See Binary Restenosis.

Severe Adverse Device Effect (*Reference: ISO 14155-2011, MEDDEV 2.7/3 12/2010*)

Adverse device effect that has resulted in any of the consequences characteristic of a SAE.

Severe Adverse Event (*Reference: ISO 14155-2011, MEDDEV 2.7/3 12/2010*)

An adverse event that causes the following situations:

Adverse event that:

- Led to death
- Led to a serious deterioration in the health of the subject that either resulted in:
 - A life-threatening illness or injury, or
 - A permanent impairment of a body structure or a body function, or
 - In-patient or prolonged hospitalization of existing hospitalization, or
 - Medical or surgical intervention to prevent life-threatening illness or injury or permanent impairment to body structure or a body function
- Led to fetal distress fetal death or a congenital abnormality or birth defect

Stent Thrombosis (*Reference: the definition of Academic Research Consortium*) (44)

Stent thrombosis should be reported as a cumulative value at the different time points and with the different separate time points. Time 0 is defined as the time point after the guide catheter has been removed and the patient left the catheterization lab.

Timing:

- Acute stent thrombosis*: 0-24 hours after stent implantation
- Subacute stent thrombosis*: >24 hours to 30 days after stent implantation
- Late stent thrombosis: >30 days to 1 year after stent implantation
- Very late stent thrombosis: >1 year after stent implantation

* Acute/subacute can also be replaced by early stent thrombosis. Early stent thrombosis is 0-30 days.

Stent thrombosis may be defined as:

- Confirmed/definite
- Probable
- Possible

Confirmed/Definite (is considered *either* angiographic confirmed or pathologic confirmed)

Angiographic confirmed stent thrombosis is considered to have occurred if:

- TIMI flow is:
 - TIMI flow grade 0 with occlusion originating in the stent or in the segment 5mm proximal or distal to the stent region in the presence of thrombus*
 - TIMI flow grade 1, 2 or 3 originating in the stent or in the segment 5mm proximal or distal to the stent region in the presence of a thrombus*

AND at least one of the following criteria, up to 48 hours, has been fulfilled:

- New onset of ischemic symptoms at rest (typical chest pain with duration >20 minutes)
- New ischemic ECG changes suggestive of acute ischemia
- Typical rise and fall in cardiac biomarkers ($>2\times$ ULN of CK)

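### Protocol Section 12 defines MI in 30-day MACE by total CK, while Section 7.1 refers the same endpoint to a CK-MB/troponin definition in Section 31.2

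*Protocol*

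**What the plan says.** Three places in the protocol bear on what counts as an MI in 30-day MACE, the primary safety endpoint.

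- **Section 12, Statistical Considerations (Safety Endpoint).** MI is given as "Q-wave and non-Q-wave myocardial infarction (total CK is two times larger than normal upper limit and MB score is positive". There is no troponin route, no ECG or ischaemia requirement and no time window.
- **Section 7.1, Primary Study Endpoint.** The same 30-day MACE carries the note "for MI definition please refer to section 31.2".
- **Section 31.2, Myocardial Infarction.** The entry opens "The definition of myocardial infarction in FAST-CTO China clinical trial". Up to 72 hours after the procedure, with a normal baseline, one criterion is "An increase in CK-MB peak to $\geq 10X$ URL during the first 48 hours following the procedure". The alternative is 5 times the limit with a new pathological Q wave or new persistent LBBB. Troponin thresholds of 70 and 35 times the limit apply only when CK-MB is unavailable. After 72 hours the rule starts from "Detection of rise and/or fall of cardiac biomarkers (CK-MB or troponin) with at least one value above the 99th percentile" and adds evidence of ischaemia.

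SAP 3.1 lists the MACE components without MI criteria and cites neither protocol section. Protocol Sections 2, 27.3 and 31.2 provide for a Clinical Events Committee (CEC) that adjudicates MI, with its procedures left to a charter. SAP Section 1 repeats that a CEC adjudicates MACE.

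**The concern.** The study is descriptive, so the 30-day MACE rate and its 95% CI are themselves the primary safety result. Two sections give that rate different MI rules, using different analytes and cut-offs. An analyst working from the statistical section would count different events from one working from the endpoint section. MACE at 6 and 12 months would inherit the same ambiguity.

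The protocol's background shows that MI can dominate this composite. In the FAST-CTO IDE trial (Section 4.3.3.3), 7 of 147 subjects had MACE and 6 of 147 had non-Q-wave MI. In the EU trial (Section 4.2.5.3), both MACE events among 42 subjects were non-Q-wave MIs.

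**Working it through.** The plan gives no figure to reproduce: the sample of 100 has no stated rate, precision target, alpha or power. The check is a comparison of the rules, followed by the effect of one subject on the rate.

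**1. The rules side by side**

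| | Section 12 | Section 31.2, MI entry |
|---|---|---|
| Biomarker | Total CK plus positive MB | CK-MB or troponin; no total CK |
| Up to 72 h, normal baseline | Total CK >2x ULN, MB positive | CK-MB ≥10x URL, or ≥5x with new Q wave or LBBB; troponin ≥70x or ≥35x with the same ECG change only if CK-MB is unavailable |
| After 72 h | Same rule | CK-MB or troponin above the 99th percentile, plus evidence of ischaemia |
| Raised baseline | Not addressed | Separate rules, again in CK-MB or troponin, such as the one beginning "In patient with elevated baseline CK-MB (or troponin) in whom the biomarker levels have not shown to be stable or decrease" |

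Section 31.2 does use a threshold of twice the upper limit for CK, but in the stent thrombosis entry, under "Typical rise and fall in cardiac biomarkers". It is not an MI criterion there.

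**2. Two hypothetical subjects** (neither has a new Q wave, so the result does not depend on whether the Section 12 parenthesis covers Q-wave MI as well as non-Q-wave MI)

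- *Subject A.* Day 1, normal baseline, total CK 3x ULN, MB positive, CK-MB 4x URL, no new Q wave or LBBB. Section 12: 3 > 2 and MB positive, so MI. Section 31.2: 4 < 5 and 4 < 10, and the troponin route is closed because CK-MB is available, so not MI.
- *Subject B.* Day 10, troponin rise above the 99th percentile with ischaemic symptoms, total CK 1.5x ULN. Section 12: 1.5 < 2, so not MI. Section 31.2: MI.

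Section 12 does not say what makes MB positive; Subject A assumes that 4x URL does. Subject B needs biomarkers from unscheduled care, because Table 11.1-1 schedules them only before the procedure and before discharge, and later contacts may be by telephone (Section 11.9).

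**3. What is collected**

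Table 11.1-1, note g, requires at least one total CK or CK-MB draw within 1 day, with CK-MB or troponin added if total CK is abnormal. Note h requires troponin if neither is drawn. Section 12 therefore cannot be applied when only CK-MB or only troponin is drawn. Section 31.2 cannot be applied from a single normal total CK.

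**4. Effect on the reported rate**

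Inputs: n = 100 (Section 12, under Hypothesis and Sample Size). The base of 5 events is an assumption. It is close to the 4.8% in both earlier trials (7/147 and 2/42), but the plan states no expected rate.

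Change in rate = (subjects added − subjects removed)/100, so one net subject = 1/100 = 1.0 percentage point.

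Exact (Clopper-Pearson) 95% limits for x events are the 2.5% quantile of Beta(x, n − x + 1) and the 97.5% quantile of Beta(x + 1, n − x):

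| Events | Rate | Exact 95% CI |
|---|---|---|
| 4/100 | 4.0% | 1.1–9.9% |
| 5/100 | 5.0% | 1.6–11.3% |
| 6/100 | 6.0% | 2.2–12.6% |

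At 5/100 the half-width is (11.28 − 1.64)/2 = 4.82 points, so one subject is 1.0/4.82 = 0.21, about a fifth of it. SAP 3.1 names no interval method. The Wilson interval at 5/100 is 2.15–11.18%, so the choice of method does not alter the point.

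**The case against.** The strongest reply is that the protocol already shows which definition it means. Section 7.1 sends the primary endpoint to Section 31.2, and the entry there presents itself as the trial's MI definition. On that reading Section 12 contains one stray parenthesis. Most of this stands: a reader might infer that the endpoint has no governing definition, and the documents do not support that. What remains is that Section 12 states a conflicting rule for the same endpoint and no passage withdraws it. Nor can Section 31.2 be assumed to control every definition. Its Technical Success entry still limits success to lesions refractory to marketed guidewires, a condition that Sections 7.1 and 12 do not contain.

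A second reply is that the CEC will settle each case. The committee reduces the risk, and its charter, which is not among the documents, may name the rule. The supplied text does not. A reader might go further and infer that site-reported MIs feed the rate, because SAP 5.4 labels its adverse event tables as site reported. That does not follow: SAP 5.4 concerns general adverse event tables, and SAP Section 1 has the CEC adjudicate MACE. The silence of SAP 3.1 on adjudicated events is a secondary clarification, not part of the contradiction.

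A third reply is that nothing can flip, because the study has no hypothesis (SAP 3.1.1). That is correct, and it limits the severity.

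**Conclusion.** The contradiction is real and sits in the current text. For the MI component of 30-day MACE, Section 12 conflicts with Section 7.1 and the Section 31.2 entry to which it refers. Section 31.2 is the likely intended definition, and SAP 3.1 does not confirm it.

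Each net reclassified subject moves the reported rate by 1.0 percentage point at the planned 100 subjects, in either direction. The intervals shown rest on an assumed 5 events. A reader might infer a particular bias, or a range of several points, but the documents give no basis for either. They contain nothing on how many subjects would fall between the rules. The two hypothetical subjects show that disagreement is possible both ways, not that it is equally likely, since Subject B depends on biomarkers taken outside the schedule. No test result or success criterion is affected. This should be fixed before analysis so that the event definition is not chosen once the data are known.

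**What to change.** Before analysis, reconcile the passages to one MI definition. In Protocol Section 12, replace the total-CK parenthesis with a reference to Section 31.2, consistent with Section 7.1, and cite the same section in SAP 3.1. As a secondary clarification, SAP 3.1 can also state whether CEC-adjudicated events make up the rate.

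No new visit or assay is needed, but there are costs:

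- Section 13 requires an amendment with IRB/EC approval before implementation when a revision affects the scientific integrity of the data. A change to a primary endpoint definition may fall under that rule, at 5 to 10 sites.
- Section 31.2 does not itself separate Q-wave from non-Q-wave MI, although Section 12 and SAP 3.1 name both. If the split is to be reported, a classification rule is needed.
- Section 31.2 judges procedural MI on peak CK-MB in the first 48 hours, while Table 11.1-1 allows a single draw within 1 day, or a normal total CK alone. The number of subjects without the CK-MB or troponin data that Section 31.2 needs should be reported alongside the rate.
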